3.1 Study Schematic

† Visits occur 3M and 6M after last injection of Bellafill (i.e., W12 initial treatment or M1 touch-up treatment) †† Visit occurs 24W after D0 (i.e., approx. 3M after W12)

4. Study Population

4.1 Number of Subjects

Approximately 45 male and/or female subjects 21 years of age or older who meet the protocol's eligibility requirements will be enrolled in the study at approximately 9 investigational sites.

4.2 Study Population Characteristics

Subjects desiring correction of their acne scarring with an injectable dermal filler will be recruited for this study.

4.3 Inclusion Criteria

1. Outpatient, male or female subjects of any race, 21 years of age or older. Female subjects of childbearing potential must have a negative urine pregnancy test result at Baseline and practice a reliable method of contraception throughout the study.

A female is considered of childbearing potential unless she is:

- postmenopausal for at least 12 months prior to study treatment administration; or
- without a uterus and/or both ovaries; or
- has been surgically sterile for at least 6 months prior to study treatment administration.

Reliable methods of contraception are:

- hormonal methods or intrauterine device in use ≥90 days prior to study treatment administration; or
- barrier methods plus spermicide in use at least 14 days prior to study treatment administration; or
- vasectomized partner.

[Exception: Female subjects of childbearing potential who are not sexually active will not be required to practice a reliable method of contraception. These subjects may be enrolled at the Investigator's discretion if they are counseled to remain sexually inactive during the study or agree to use an approved method of contraception should they become sexually active and understand the possible risks in getting pregnant during the study.]

- 2. Negative response to the Bellafill Skin Test.
- 3. Presence of ≥4 distensible atrophic acne scars located within the facial treatment area. Subject desires correction of his/her atrophic acne scarring.
- 4. All Fitzpatrick skin types are eligible.
- 5. Subjects with a history of HSV-1 (oral herpetic outbreak) willing to accept prophylactic treatment with antiviral medication.
- 6. Willing to withhold additional aesthetic therapies to the proposed treatment area (e.g., other soft tissue fillers such as hyaluronic acid, and/or any resurfacing procedures (as described in Protocol Section 5.3) for the duration of the study.

- 7. Able to follow study instructions and likely to complete all required visits, as assessed by the Investigator.
- 8. Sign an IRB-approved Informed Consent Form, Photographic Release Form, and the Authorization for Use and release of Health and Research Study Information (HIPAA) Form prior to any study-related procedures being performed.

[figure not shown]
4.4 Exclusion Criteria

- 1. Female subjects that are pregnant (positive urine pregnancy test), breast-feeding, or who are of childbearing potential and not practicing a reliable method of birth control.
- Undergone facial treatments with any prohibited treatment/procedures and/or use of any other prohibited treatment/procedure within certain time periods as listed in Protocol Section 5.3.
- 3. Excisional facial surgery (such as Blepharoplasty, Face Lift, Rhinoplasty) of the face ≤ 6 months prior to study enrollment or plans for facial surgery during the study.
- 4. History of bleeding disorders.
- 5. Presence of any skin pathology or condition that could interfere with the evaluation of the treatment areas, worsen due to the proposed treatment or require interfering topical, systemic or surgical therapy.
- 6. Recent or current history of inflammatory skin disease, infection, cancerous/precancerous lesion, unhealed wound or clinically significant acne in the proposed treatment areas. Clinically significant acne is defined as a patient whom has ≥3 active inflammatory acne lesions in the treatment areas.
- 7. History of systemic granulomatous diseases active or inactive (e.g., Sarcoid, Wegeners, TB) or connective tissue diseases (e.g., lupus, dermatomyositis).
- 8. Hypertrophic acne scars, any evidence of keloid scarring in the treatment area.
- 9. Known hypersensitivity or previous allergic reaction to any of the components of the study device (including lidocaine or any amide-based anesthetic), or has a history of allergies to any bovine collagen products, including but not limited to injectable collagen, collagen implants, hemostatic sponges, and collagen-based sutures.
- 10. Undergone or be planning to undergo desensitization injections to meat products.
- 11. Unable to communicate or cooperate with the Investigator due to a language barrier (non-English speaking), poor mental development, or impaired cerebral function.
- 12. Evidence of alcohol or drug abuse (Investigator opinion), or history of poor cooperation, non-compliance with medical treatment, or unreliability.
- 13. Use of an investigational device, biologic or drug in the past 30 days, or be currently participating in an experimental drug, biologic or device trial.
- 14. Exhibits additional physical attributes which prevent the assessment or treatment of the atrophic scars, as judged by the Investigator, such as excessive hair, traumatic or surgical scars, excessive hyperpigmentation in the treatment area, etc.
- 15. Has a condition or be in a situation that, in the Investigator's opinion, may put the subject at significant risk, may confound the study results, or may interfere significantly with the subject's participation in the study.
- 16. An employee (or a relative of an employee) of the Investigator, Sponsor or representative of the Sponsor.

5. Methods

5.1 Treatment Area

On each side of the face, the **treatment area** is defined inferiorly by the mandibular ridge and ramus, medially by the nasolabial fold and a line drawn directly inferior from the oral commissure, laterally by the tragus and pinna and superiorly by an imaginary line drawn from the lateral canthus to the top of the pinna where it attaches to the face, as per the following diagram:

5.2 Study Treatments

Microneedling Treatment: All eligible scars within the treatment areas on each side of the face will receive microneedling treatment. The device will be rolled in a horizontal direction with medium pressure. After every roll, the device will be lifted and positioned a few millimeters inferior to the previous starting point. Rolling will be repeated until the entire skin area has been treated. The device will then be reoriented vertically and rolling will be repeated in a vertical direction. See Appendix 2 for additional instructions.

Bellafill Treatment: At Visit 4, all eligible scars within the treatment areas on each side of the face will be treated. Bellafill should be injected using a standard tunneling technique whereby the filler is injected in a retrograde manner utilizing several passes until the scar reaches a desired level of correction. A touch-up treatment is allowed at Visit 5B (Month 1 after randomization) if additional treatment is required to achieve optimal correction. The total treatment volume of Bellafill used per subject is dependent on the number and size of scars treated; however, the maximal volume of Bellafill to be injected in a subject is 8.9 ml.

5.3 Prohibited Treatment/Procedures

Use of other soft tissue fillers in the face and/or concurrent administration of other aesthetic treatments of the face during the study are prohibited (e.g., lasers, implants, peels, microdermabrasion, etc.). Other necessary therapies that will not interfere with the response to treatment may be provided to the subject at the discretion of the Investigator.

Use of the following medications/procedures (concurrent and contraindicated treatments) have either restrictions for usage, or are prohibited during the course of the study and appropriate wash-out periods noted below must be respected:

!	Hyaluronic acid such as:	
	Juvederm, Restylane, Belotero	
	o Voluma, Restylane Lyft	
,	Hydroxylapatite	
!	Polylactic acid	
!	Porcine or human collagen	
į.	Autologous fat	12 months prior to BL Visit
!	Bellafill	
	Prohibited Treatment: Any past use of a permane (e.g., polyacrylamide, polyethylene oxide, silicone	•
Cuata		,
Jysie	emic Medications Accutane	10 months prior to PL Visit
	Accularie	12 months prior to BL Visit
·		17 days are ty
!	Corticosteroiods (e.g., prednisone) or Interferon	
!!	Corticosteroiods (e.g., prednisone) or Interferon Anti-coagulation therapy (e.g., warfarin)	. ≤ 14 days pre-tx
! ! !	Corticosteroiods (e.g., prednisone) or Interferon Anti-coagulation therapy (e.g., warfarin) NSAIDs, ASA, or >30,000IU/day oral vitamin E	. ≤ 14 days pre-tx
! ! ! ! Proce	Corticosteroiods (e.g., prednisone) or Interferon Anti-coagulation therapy (e.g., warfarin) NSAIDs, ASA, or >30,000IU/day oral vitamin E edures in the face, scalp or neck	. ≤ 14 days pre-tx
! ! ! ! Proce	Corticosteroiods (e.g., prednisone) or Interferon Anti-coagulation therapy (e.g., warfarin) NSAIDs, ASA, or >30,000IU/day oral vitamin E	. ≤ 14 days pre-tx
! ! ! ! ! ! !	Corticosteroiods (e.g., prednisone) or Interferon Anti-coagulation therapy (e.g., warfarin) NSAIDs, ASA, or >30,000IU/day oral vitamin E edures in the face, scalp or neck Cutaneous or RF laser treatment Intense-pulsed light treatment	. ≤ 14 days pre-tx ≤ 7 days pre-tx or ≤ 7 days post-tx
! ! ! ! ! ! !	Corticosteroiods (e.g., prednisone) or Interferon Anti-coagulation therapy (e.g., warfarin) NSAIDs, ASA, or >30,000IU/day oral vitamin E edures in the face, scalp or neck Cutaneous or RF laser treatment	. ≤ 14 days pre-tx ≤ 7 days pre-tx or ≤ 7 days post-tx
! ! ! ! ! ! ! !	Corticosteroiods (e.g., prednisone) or Interferon Anti-coagulation therapy (e.g., warfarin) NSAIDs, ASA, or >30,000IU/day oral vitamin E edures in the face, scalp or neck Cutaneous or RF laser treatment Intense-pulsed light treatment	. ≤ 14 days pre-tx ≤ 7 days pre-tx or ≤ 7 days post-tx ent
! ! ! Proce ! ! !	Corticosteroiods (e.g., prednisone) or Interferon Anti-coagulation therapy (e.g., warfarin) NSAIDs, ASA, or >30,000IU/day oral vitamin E edures in the face, scalp or neck Cutaneous or RF laser treatment Intense-pulsed light treatment Photodynamic therapy or Photomodulation treatm Botulinum toxin injection (injections of the trunk or Prescription strength topical retinoids (tretinoin, ac	ent extremities permitted) dapalene, tazarotene) ≤ 14 days pre-tx ≤ 7 days post-tx 6 months prior to BL Visit
Proce	Corticosteroiods (e.g., prednisone) or Interferon Anti-coagulation therapy (e.g., warfarin) NSAIDs, ASA, or >30,000IU/day oral vitamin E edures in the face, scalp or neck Cutaneous or RF laser treatment Intense-pulsed light treatment Photodynamic therapy or Photomodulation treatm Botulinum toxin injection (injections of the trunk or	ent extremities permitted) dapalene, tazarotene) ≤ 14 days pre-tx ≤ 7 days post-tx 6 months prior to BL Visit
Proce ! ! ! ! ! ! ! ! ! ! ! ! ! ! ! ! ! ! !	Corticosteroiods (e.g., prednisone) or Interferon Anti-coagulation therapy (e.g., warfarin) NSAIDs, ASA, or >30,000IU/day oral vitamin E edures in the face, scalp or neck Cutaneous or RF laser treatment Intense-pulsed light treatment Photodynamic therapy or Photomodulation treatm Botulinum toxin injection (injections of the trunk or Prescription strength topical retinoids (tretinoin, ac	ent extremities permitted) lapalene, tazarotene) es within treatment area(s) ≤ 14 days pre-tx ≤ 7 days post-tx 6 months prior to BL Visit

All treatment/procedures received by the subject within 30 days prior to the baseline visit and throughout the treatment period must be recorded in the electronic Case Report Form (eCRF) with end dates, if applicable.

If prohibited therapies are administered during the study period, subject participation will not automatically be discontinued. The event will be documented by the site staff as a protocol deviation, and depending upon the nature of the prohibited therapy and the timing relative to the determination of the primary endpoint, the Sponsor may make a decision to discontinue the subject.

The decision to administer a prohibited medication/treatment is done with the safety of the study subject as the primary consideration. If the permissibility of a specific medication/treatment is in question, the ethica CRO Project Manager should be contacted before the prohibited medication/treatment is administered.

6. Materials

Bellafill: Commercially available Bellafill and Bellafill Skin Tests will be used (see Skin Test IFU and Bellafill IFU in Appendix 3 and 4, respectively).

Microneedling Dermarollers: Commercially available microneedling dermarollers will be provided by Suneva Medical.. Length will be 1.5mm.

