- The safety and effectiveness of Bellafill for nasolabial fold wrinkles and cheek acne scars have not been established in patients under the age of 21 years. There is limited information on the safety of Bellafill in patients less than 36 years of age.

In the pivotal Acne Scar Study of Bellafill, the incidence of injection site reactions in subjects less than 36 years old (30 subjects) was similar to the incidence in subjects above the age of 36 (113 subjects). The majority of these injection site reactions were mild in severity.

- The safety in patients with known susceptibility to hyperpigmentation, keloid formation and hypertrophic scarring has not been studied. Formation of hyperpigmentation, keloids or hypertrophic scars may occur after dermal filler injections including Bellafill. In the pivotal Acne Scar Study of Bellafill, the incidence and severity of adverse events in 34 subjects with Fitzpatrick Skin Types V and VI was similar to that reported in 109 patients with Fitzpatrick Skin types I-IV and no unique adverse events associated with these patient subgroups were observed.
- As with all transcutaneous procedures, Bellafill injection carries a risk of infection. The usual precautions associated with injectable materials should be followed.
- The safety of Bellafill in patients on immunosuppressive therapy has not been established.
- The safety of Bellafill in patients with connective tissue disorder has not been established.
- Bruising or bleeding may occur at Bellafill injection sites. Use of Bellafill in patients who have undergone therapy with thrombolytics, anticoagulants, or inhibitors of platelet aggregation within 3 weeks preceding treatment has not been studied.
- Patients should minimize exposure of the treated area to excessive sun, UV-lamp exposure and extreme cold weather at least until any initial swelling and redness has resolved.
- If laser treatment, chemical peeling or any other procedure based on active dermal response is considered after treatment with Bellafill, there is a possible risk of eliciting an inflammatory reaction at the implant site. This also applies if Bellafill is administered before the skin has healed completely after such a procedure.
- The use of Bellafill in anatomical spaces other than the dermis for correction of
 nasolabial folds and for acne scars on the cheek has not been studied. Refer to the
 Clinical Studies section for more information on implantation sites that have been
 studied.

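### Section 5.3 appears to restrict anticoagulants for a shorter period, and to list fewer drug classes, than the three-week precaution in the appended Bellafill label, and nothing reconciles the two for the injection visits

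*Combined protocol and SAP*

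**What the plan says.** Section 5.3 introduces its list by saying that the items "have either restrictions for usage, or are prohibited during the course of the study and appropriate wash-out periods noted below must be respected". The block on systemic medications contains the adjacent rows "Anti-coagulation therapy (e.g., warfarin) NSAIDs, ASA, or >30,000IU/day oral vitamin E". The windows that follow in reading order are "≤ 14 days pre-tx ≤ 7 days pre-tx or ≤ 7 days post-tx". That string joins cells that were separate in the table, so matching 14 days to anticoagulants and 7 days to NSAIDs, aspirin and vitamin E is an inference from row order.

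The Bellafill instructions for use form Appendix 4, are cited in Section 6 and must be kept in the study files under Section 13.4. Their Precautions section warns that "Bruising or bleeding may occur at Bellafill injection sites". It then says that use in patients who have had "thrombolytics, anticoagulants, or inhibitors of platelet aggregation within 3 weeks preceding treatment has not been studied".

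Section 10.5 separately tells subjects to avoid NSAIDs for at least 24 hours after treatment. Exclusion 4 covers a history of bleeding disorders, not drug exposure. Sections 10.2.4 and 10.3.1 (Visits 4 and 5a) require concomitant medication to be recorded but list no check of a washout.

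**The concern.** Two parts of one protocol deal with the same bleeding-related drugs before the same injection, and they differ in length and in scope. Elsewhere the protocol follows the label closely. Exclusions 4, 9 and 10 track its contraindications, and the 8.9 ml volume cap in Section 5.2 equals the label's 8.9 cc. A shorter drug window with no stated reason therefore looks unintended.

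Subject safety comes first: a site could follow Section 5.3 exactly and inject someone for whom the label offers no data. Interpretation comes second. Only Track A is injected, at up to two visits, so any drug-related bruising or bleeding at injection sites would sit on one side of a comparison of roughly 22 subjects per track (45/2) and could be read as an effect of Bellafill.

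**Working it through.** The plan gives no figure to reproduce. The check is a day count.

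**Inputs**
- Section 5.3, row order: anticoagulants 14 days before treatment; NSAIDs/aspirin 7 days before and 7 days after.
- Appendix 4, Precautions: 3 weeks = 21 days before treatment.
- Section 10.1: last microneedling at Week 6 (day 42), Visit 4 at Week 12 (day 84), Visit 5a one 28-day month later (day 112), with a window of ±1 week.
- Assumption: the pre-treatment windows apply to each Bellafill session. The table counts other rows from the baseline visit, so treatment appears to mean something different here.

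**Formula.** Days inside the label period that Section 5.3 leaves open = 21 − (Section 5.3 window), less any days covered by the post-treatment restriction after the previous session.

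| Session | Row | Label period | Closed by Section 5.3 | Left open | Days |
|---|---|---|---|---|---|
| Visit 4, day 84 | Anticoagulants | 63–83 | 70–83 | 63–69 | 7 |
| Visit 5a, day 112 | Anticoagulants | 91–111 | 98–111 | 91–97 | 7 |
| Visit 5a, day 105 | Anticoagulants | 84–104 | 91–104 | 85–90 | 6 |
| Visit 4, day 84 | NSAIDs/aspirin | 63–83 | 77–83 | 63–76 | 14 |
| Visit 5a, day 112 | NSAIDs/aspirin | 91–111 | 91 and 105–111 | 92–104 | 13 |
| Visit 5a, day 105 | NSAIDs/aspirin | 84–104 | 85–91 and 98–104 | 92–97 | 6 |

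Day 84 is the previous injection day and is not counted. The NSAID/aspirin rows are conditional: they matter only if these drugs are counted as inhibitors of platelet aggregation.

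**Sensitivity to the damaged table.** The day-based values in the block are 7, 14 and a garbled entry beside the corticosteroid row that may read 17. Applied to anticoagulants at Visit 4 they give 21 − 7 = 14, 21 − 14 = 7 and 21 − 17 = 4 days. All are below 21, so a gap remains at Visit 4 whichever value belongs to the row. For NSAIDs/aspirin at an early Visit 5a (day 105), a 14- or 17-day reading leaves no gap.

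**Scope.** The label names three classes. The legible Section 5.3 list has "Anti-coagulation therapy (e.g., warfarin" and "NSAIDs, ASA, or >30,000IU/day oral vitamin E". Thrombolytics and platelet inhibitors as a class are not in it.

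**Restricted or prohibited.** If anticoagulants belong to the group barred for the whole study, the anticoagulant gap at both visits is zero. A window expressed as days before treatment reads more naturally as a restriction around treatment, but the text does not settle it.

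**The case against.** The case for leaving the plan alone has four parts.

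- **The label sentence is neither a washout nor a contraindication.** It says only that such use has not been studied. This stands. A reader might infer that Section 5.3 breaches a label prohibition, and the documents do not support that. What remains is an unexplained difference between two parts of the protocol.
- **The aspirin/NSAID comparison.** A reader might present 7 against 21 days as a three-fold shortfall. The label's wording is "anticoagulants, or inhibitors of platelet aggregation within 3 weeks preceding treatment has not been studied"; it names neither aspirin nor NSAIDs. That comparison rests on a classification the documents do not make, so it can only be conditional. The anticoagulant comparison needs no such step.
- **Size.** A reader might multiply an assumed rate of drug use by Track A's 22 or so subjects, or cite the label's diary figure of bruising in 77/130 (59.2%). Neither measures this gap. The relevant subjects are those whose last use fell in a particular stretch of days, and no document gives their number. The diary rate is not broken down by drug use. Bruising is also a common treatment response under Section 11.1.2 and becomes an adverse event only if excessive and clinically significant, so most extra bruising would never reach the adverse event tables.
- **Other safeguards.** Exclusion 15 allows investigator judgement, Section 5.3 sends permissibility questions to the CRO, and sites hold the label. These help, but they depend on someone noticing that a subject who passes Section 5.3 needs a second look. They do not reliably close the gap.

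**Conclusion.** The mismatch is real and modest. On the row-order reading, Section 5.3 leaves 7 days open for anticoagulants at Visit 4 and 6 to 7 days at Visit 5a (nominal or one week early) that fall inside the label's unstudied period. Its legible list also omits thrombolytics and platelet inhibitors as a class. The length of the gap rests on the row order of a damaged table and on anticoagulants being restricted rather than barred throughout. The first assumption affects its size at Visit 4 (4 to 14 days across the possible values) but not its existence; the second could remove it for anticoagulants. An extension to aspirin and NSAIDs is possible but unproven. The number of subjects affected, and any effect on bleeding rates, cannot be estimated from the documents. It merits correction because it bears on subject safety and costs little to resolve.

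**What to change.** The sponsor should reconcile Section 5.3 with the Appendix 4 precaution for the Bellafill visits (Visit 4 and Visit 5a). That means stating the drug list, the window for each item, and whether each item is restricted around treatment or prohibited for the whole study. If the protocol departs from the label on purpose, it should give the reason. The post-treatment NSAID entry in Section 5.3 (apparently 7 days) and the minimum of 24 hours in Section 10.5 should be reconciled at the same time. This review does not propose a window.

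In Section 12.3, add a listing that identifies Track A adverse events in subjects whose concomitant medication shows a drug in these classes within the label's stated period before an injection. The planned medication listing already carries treatment, start and stop dates, so no new data are needed. It will not capture bruising treated as a common treatment response.

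The cost is a clarification to one table and a small listing task. A few visits might need rescheduling, depending on how the sponsor resolves the difference.

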6.1 Packaging, Labeling and Storage

Open label commercially packaged supplies of dermarollers and Bellafill will be provided to Investigators. Bellafill is to be stored at standard domestic refrigerator temperature.

